DMC	data monitoring committee
ECG	electrocardiogram
ECMO	extracorporeal membrane oxygenation
eCRF	electronic case report form
eGFR	estimated glomerular filtration rate
ESR	erythrocyte sedimentation rate
ET	endotracheal tube
FAS	Full Analysis Set
FiO ₂	fraction of inspired oxygen
Gilead	Gilead Sciences
HIV	human immunodeficiency virus
HLT	high-level term
IAP	interim analysis plan
Ig	immunoglobulin
IL-6	Interleukin-6
INR	international normalized ratio
IV	intravenous
LPV	lopinavir
LOD	limit of detection
LOQ	limit of quantitation
MAP	mean arterial pressure
MedDRA	Medical Dictionary for Regulatory Activities
PaO ₂	partial pressure of oxygen
PCR	polymerase chain reaction
РСТ	procalcitonin
PEWS	Pediatric Early Warning Score

PK	pharmacokinetic(s)
PS	Patient Safety
РТ	preferred term
РТ	prothrombin time
PTT	partial thromboplastin time
Q1, Q3	first quartile, third quartile
RDV	remdesivir (GS-5734 TM)
RT-qPCR	reverse transcriptase quantitative polymerase chain reaction
SAE	serious adverse event
SAP	statistical analysis plan
SARS	severe acute respiratory syndrome
SBECD	sulfobutylether β-cyclodextrin sodium
SD	standard deviation
SE	Standard error
SOC	system organ class
SpO ₂	peripheral oxygen saturation
TEAE	treatment-emergent adverse event
TFLs	tables, figures, and listings
ULN	upper limit of normal
US	United States

PHARMACOKINETIC ABBREVIATIONS

AUC _{last}	area under the concentration versus time curve from time zero to the last quantifiable concentration
AUC _{tau}	area under the concentration versus time curve over the dosing interval
Clast	last observed quantifiable concentration of the drug
C _{max}	maximum observed concentration of drug
C _{tau}	observed drug concentration at the end of the dosing interval
CL _{ss} /F	apparent oral clearance after administration of the drug:
	at steady state: $CL_{ss}/F = Dose/AUC_{tau}$, where "Dose" is the dose of the drug
t _{1/2}	estimate of the terminal elimination half-life of the drug, calculated by dividing the natural log of 2 by the terminal elimination rate constant (λ_z)
T _{last}	time (observed time point) of C _{last}
T _{max}	time (observed time point) of C _{max}
Vz	volume of distribution of the drug after intravenous administration
V_z/F	apparent volume of distribution of the drug
λz	terminal elimination rate constant, estimated by linear regression of the terminal elimination phase of the concentration of drug versus time curve

1. INTRODUCTION

This statistical analysis plan (SAP) describes the statistical analysis methods and data presentations to be used in tables, figures, and listings (TFLs) in the final analysis clinical study report (CSR) for Study GS-US-540-5823. This SAP is based on the study protocol amendment 4.0 dated 06 January 2022, the country specific protocol amendment 4.1 dated 10 February 2022, and the electronic case report form (eCRF). The SAP will be finalized before database finalization. Any changes made after the finalization of the SAP will be documented in the CSR.

1.1. Study Objectives

The primary objective of this study is as follows:

- To evaluate the safety and tolerability of remdesivir (RDV; GS-5734TM) in participants with laboratory-confirmed COVID-19 aged 0 days to < 18 years
- To evaluate the pharmacokinetics (PK) of RDV in participants with laboratory-confirmed COVID-19 aged 0 days to < 18 years

The secondary objectives of this study are as follows:

- To evaluate the efficacy of RDV in participants with laboratory-confirmed COVID-19 aged 0 days to < 18 years
- To determine the antiviral activity of RDV in participants with laboratory-confirmed COVID-19 aged 0 days to < 18 years
- To evaluate the change from baseline in oxygenation use
- To evaluate the change from baseline in the use of mechanical ventilation or extracorporeal membrane oxygenation (ECMO)
- To evaluate clinical improvement using the Pediatric Early Warning Score (PEWS) scale in participants with laboratory-confirmed COVID-19 aged 0 days to < 18 years
- To determine sulfobutylether β-cyclodextrin sodium (SBECD) exposures (where possible)
- To provide data on use of medications other than RDV for treatment of COVID-19

The exploratory objectives of this study are as follows:

1.2. Study Design

This is a Phase 2/3 single-arm, open-label study of the safety, tolerability, PK, and efficacy of RDV in pediatric participants from birth to < 18 years of age with laboratory-confirmed infection with COVID-19 (refer to the protocol for complete inclusion and exclusion criteria).

At least 52 participants aged 0 days to < 18 years will be enrolled as described in the table below.

Cohort	Description	Dose	Number of participants
Pediatric participants ≥ 28 days to < 18 years old			
1	\geq 12 years to < 18 years and weight \geq 40 kg	IV RDV 200 mg on Day 1 followed by IV RDV 100 mg daily up to 10 days	12
2	≥ 28 days to < 18 years and weight ≥ 20 kg to < 40 kg	IV RDV 5 mg/kg on Day 1 followed by IV RDV 2.5 mg/kg	12
3	≥ 28 days to < 18 years and weight $\geq 12~kg$ to < 20 kg	daily up to 10 days	12
4	\ge 28 days to < 18 years and weight \ge 3 kg to < 12 kg		12
Term neo	onatal participants 0 days to < 28 days old		
5	\geq 14 days to < 28 days of age, gestational age > 37 weeks and weight at screening \geq 2.5 kg	IV RDV 5 mg/kg on Day 1 followed by IV RDV 2.5 mg/kg daily up to 10 days	≥4
6	0 days to < 14 days of age, gestational age > 37 weeks and birth weight ≥ 2.5 kg	IV RDV 2.5 mg/kg on Day 1 followed by IV RDV 1.25 mg/kg daily up to 10 days	All available
Preterm 1	neonates and infants 0 days to < 56 days old		
7	0 days to < 56 days of age, gestational age \leq 37 weeks and birth weight \geq 1.5 kg	IV RDV 2.5 mg/kg on Day 1 followed by IV RDV 1.25 mg/kg daily up to 10 days	All available
	CI		

Table 1-1.Study Design

 $RDV = remdesivir (GS-5734^{TM})$

Participants must:

- Have COVID-19 confirmed by polymerase chain reaction (PCR) via a validated assay at a local laboratory
- Be hospitalized and requiring medical care for COVID-19

Participants in Cohorts 1-8 who meet eligibility criteria will be enrolled on Day 1 into a single arm of RDV using an interactive web response system, and assigned a subject number. Randomization and treatment codes are not applicable in this study. Blinding of treatment assignments or data is not applicable in this study.

Participants in Cohorts 1-5 will be enrolled in parallel. Participants in Cohorts 6 and 7 will only be enrolled once RDV exposures have been evaluated from Cohort 5 and a dose has been determined. There is no minimum number of participants to be enrolled in Cohorts 6 and 7 due to the rarity of such participants. CCI

Participants will be treated for up to 10 days. Those participants who have demonstrated clinical improvement may be considered for a shorter treatment period.

Screening is to be completed within 2 days prior to the Day 1 visit.

At the screening visit and all subsequent study visits (or until hospital discharge - whichever comes first) laboratory analyses (hematology, chemistry, inflammatory markers, urinalysis, and routine coagulation test), vital signs (heart rate, temperature, blood pressure [mean arterial pressure if available, systolic and diastolic], respiratory rate [if not on a ventilator], oxygen saturation), complete or symptom-directed physical examinations will be performed. Nasopharyngeal and oropharyngeal samples (combined) OR nasal and oropharyngeal samples (combined), and rectal or fecal swab will be collected on Days 1, 3, 5, 7, and 10 (if feasible) for SARS-CoV-2 reverse transcriptase quantitative polymerase chain reaction (RT-qPCR) viral load testing and possible viral resistance testing. Endotracheal tube aspirates will also be collected if the participant is intubated. If the participant is discharged prior to Day 10, the samples for SARS-CoV-2 RTqPCR viral load testing and possible viral resistance testing and possible viral resistance testing can be collected by assigned study staff at the participant's home or as an outpatient on the assigned days noted above, if feasible. Serum for SARS-CoV-2 IgG, IgM, and IgA serology will be collected at Screening, Day 5, Day 10 (if feasible), and the Day 30 Follow-up visit (for participants weighing ≥ 12 kg).

Clinical scoring using PEWS and the Ordinal Scale will occur at Screening and daily through the duration of dosing.

Adverse events and concomitant medications will be assessed from Screening through the Day 30 Follow-up visit.

As many of the specified sparse PK assessments should be obtained from each participant as is feasible.

1.3. Sample Size and Power

The total sample size will be at least 52 participants.

Twelve (12) participants for each cohort (Cohorts 1-4) will be enrolled in this study. Pharmacokinetic data from these participants will provide >99% power for each cohort to conclude exposure equivalence of RDV AUC_{tau} in adolescents and children vs. 25 healthy adult participants in GS-US-399-5505 study (see Table 1-2) using two one-sided tests with each performed at an alpha level of 0.05. In this power analysis, it is assumed that the expected geometric mean ratio of AUC_{tau} between the adolescents and children group vs. the adult group is equal to 1, the inter-participant standard deviation (SD) (natural log scale) of AUC_{tau} is 0.18, and the equivalency boundary is 70% to 143%.

Meanwhile, twelve (12) participants from each cohort (Cohorts 1-4) will also provide >99% power to conclude exposure equivalence of RDV C_{max} in adolescents and children, compared to 26 healthy adult participants in GS-US-399-5505 study (see Table 1-2), assuming the expected geometric mean ratio of C_{max} between the adolescents and children group and the adult group is equal to 1, the inter-participant SD (natural log scale) of C_{max} is 0.19, and the equivalency boundary is 70% to 143%.

Sample size and power calculations were made using the software package nQuery Advisor(R) Version 8.5.

Table 1-2. Remdesivir, Nucleoside Metabolite GS-441524, and GS-704277 Plasma PK Parameters by Dose Following 30-Minute IV Infusion(s) of Remdesivir in Healthy Adult Participants in GS-US-399-5505

Study	GS-US-399-5505			
	Multiple RDV Dose (100mg)			
PK Parameter ^a		Day 5 and 10		
		$N = 26^{b}$		
Plasma RDV	Remdesivir	GS-441524 Metabolite	GS-704277 Metabolite	
C _{max} (ng/mL)	2228.8 (19.2)	145.0 (19.3)	245.5 (33.9)	
C _{tau} (ng/mL)		69.2 (18.2)		
C _{last} (ng/mL)	8.1 (46.9)	12.2 (50.0)	3.9 (27.5)	
T _{max} (h)	0.68 (0.25, 0.75)	1.51 (1.50, 2.00)	0.75 (0.75, 0.78)	
T _{last} (h)	4.00 (4.00, 4.02)	96.00 (96.00, 96.00)	8.00 (8.00, 8.00)	
t _{1/2} (h) ^d	0.96 (0.86, 1.08)	27.36 (25.29, 30.32)	1.23 (1.15, 1.38)	
AUC _{last} (h·ng/mL)	1562.8 (17.0)	4189.3 (17.7)	454.4 (31.8)	
AUC _{tau} (h·ng/mL)	1585.3 (16.6)	2229.2 (18.4)	461.5 (31.4)	
CL _{ss} (mL/h)	65068.7 (19.8)			
V _z (mL)	92557.2 (29.5)			

% CV = percentage coefficient of variation; IV = intravenous; PK = pharmacokinetic; Q1 = first quartile; Q3 = third quartile; $RDV = remdesivir (GS-5734^{TM})$

Certain parameters are missing since Lambda_z is not reliably estimable.

а Data are presented as mean (%CV), except for T_{max} , T_{last} , and $t_{1/2}$, which are presented as median (Q1, Q3).

b N = 25 for AUC_{tau}, $t_{1/2}$, CLss, and Vz

c N = 25 for C_{tau} and N = 20 for $t_{1/2}$ Source: GS-US-399-5505 Final CSR Table 15.10.1.1.6.1, 15.10.1.1.6.3, 15.10.1.1.6.2, 15.10.1.1.6.4.

2. TYPE OF PLANNED ANALYSIS

2.1. Interim Analyses

Prior to the final analysis, an interim analysis was conducted to support the submission of applications to extend the indication for RDV to include pediatric participants 28 days of age and older weighing at least 3kg. The interim analysis was performed after (i) all participants in Cohorts 1-4 had been enrolled and had completed the study or prematurely discontinued from the study, (ii) participants in Cohort 8 as of the last date of enrolment into Cohorts 1-4 had completed the study or prematurely discontinued from the study, (ii) outstanding data queries had been resolved or adjudicated as unresolvable, and (iv) the data had been cleaned and finalized.

The Interim Analysis Plan (IAP) describes the analysis plan for the Cohorts 1-4 and 8 interim analysis.

2.1.1. DMC Analysis

An external multidisciplinary Data Monitoring Committee (DMC) reviewed safety, PK, and efficacy data after the first 27 enrolled participants in Cohorts 1-4 had completed the study or prematurely discontinued from the study.

The DMC reviewed the safety, PK, and efficacy data and determined that the study could continue according to the protocol without modification. More details are documented in the DMC charter.

2.2. Final Analysis

The final analysis will be performed after all participants have completed the study, outstanding data queries have been resolved or adjudicated as unresolvable, and the data have been cleaned and finalized.

3. GENERAL CONSIDERATIONS FOR DATA ANALYSES

Analysis results will be presented using descriptive statistics. For categorical variables, the number and percentage of participants in each category will be presented; for continuous variables, the number of participants (n), mean, SD or standard error (SE), median, first quartile (Q1), third quartile (Q3), minimum, and maximum will be presented. For PK analyses, the geometric mean, 95% confidence interval (CI) of the geometric mean, and the mean and SD of the natural log-transformed values will also be provided, if appropriate.

By-participant listings will be presented for all participants in the All Enrolled Analysis Set and sorted by subject identifier (ID) number, visit date, and time (if applicable). Data collected on log forms, such as adverse events (AEs), will be presented in chronological order within the participant. The cohort group to which participants were initially assigned will be used in the listings. Age, sex at birth, race, and ethnicity will be included in the listings, as space permits.

3.1. Analysis Sets

Analysis sets define the participants to be included in an analysis. Analysis sets and their definitions are provided in this section. Participants included in each analysis set will be determined before database finalization for final analysis. The analysis set will be identified and included as a subtitle of each table, figure, and listing.

A summary of the number and percentage of participants in each analysis set will be provided by cohort and overall total.

3.1.1. All Enrolled Analysis Set

The All Enrolled Analysis Set includes all participants who are enrolled into the study. This is the primary analysis set for by-participant listings.

3.1.2. Full Analysis Set

The Full Analysis Set (FAS) includes all enrolled participants who received at least 1 dose of study drug. This is the primary analysis set for efficacy analyses.

3.1.3. Safety Analysis Set

The Safety Analysis Set includes all enrolled participants who received at least 1 dose of study drug. This is the primary analysis set for safety analyses.

3.1.4. Pharmacokinetic Analysis Set

The RDV PK analysis set includes all enrolled participants who received at least 1 dose of RDV and for whom PK concentrations of RDV are available.

The SBECD PK analysis set includes all enrolled participants who received at least 1 dose of RDV and for whom PK concentrations of SBECD are available.

3.2. Subject Grouping

Participants will be analyzed based on the cohort group to which they were initially assigned as well as overall.

3.3. Strata and Covariates

This study does not use a stratified randomization schedule when enrolling participants. No covariates will be included in efficacy and safety analyses.

3.4. Examination of Subject Subgroups

There are no prespecified subject subgroupings for efficacy and safety analyses.

3.5. Multiple Comparisons

Adjustments for multiplicity will not be made, because no formal statistical testing will be performed in this study.

3.6. Missing Data and Outliers

3.6.1. Missing Data

In general, missing data will not be imputed unless methods for handling missing data are specified. Exceptions are presented in this document.

Missing pre-treatment laboratory results will be treated as normal (ie, no toxicity grade) for the laboratory abnormality summary. The handling of missing or incomplete dates for AE onset is described in Section 7.1.5.2, and for prior and concomitant medications in Section 7.4.

3.6.2. Outliers

Outliers will be identified during the data management and data analysis process, but no sensitivity analyses will be conducted. All data will be included in the data analysis, unless specified otherwise.

3.7. Data Handling Conventions and Transformations

The following conventions will be used for the imputation of date of birth when it is partially missing or not collected:

- If only month and year of birth is collected, then "15" will be imputed as the day of birth
- If only year of birth is collected, then "01 July" will be imputed as the day and month of birth
- If year of birth is missing, then date of birth will not be imputed.

In general, age collected at Day 1 (in years) will be used for analyses and presented in listings. If age at Day 1 is not available for a participant, then age derived based on date of birth and the Day 1 visit date will be used instead. If an enrolled participant was not dosed with any study drug, the enrollment date will be used instead of the Day 1 visit date. For screen failures, the date the first informed consent was signed will be used for the age derivation. Age required for longitudinal and temporal calculations and analyses (e.g., estimates of creatinine clearance, age at date of AE) will be based on age derived from date of birth and the date of the measurement or event, unless otherwise specified.

Laboratory data that are continuous in nature but are less than the lower limit of quantitation (LOQ) or above the upper LOQ will be imputed as follows:

- A value that is 1 unit less than the lower LOQ will be used to calculate descriptive statistics if the datum is reported in the form of "< x" (where x is considered the lower LOQ). For example, if the values are reported as < 50 and < 5.0, values of 49 and 4.9, respectively, will be used to calculate summary statistics. An exception to this rule is any value reported as < 1 or < 0.1, etc. For values reported as < 1 or < 0.1, a value of 0.9 or 0.09, respectively, will be used to calculate summary statistics.
- A value that is 1 unit above the upper LOQ will be used to calculate descriptive statistics if the datum is reported in the form of "> x" (where x is considered the upper LOQ). Values with decimal points will follow the same logic as above.
- The lower or upper LOQ will be used to calculate descriptive statistics if the datum is reported in the form of "≤ x" or "≥ x" (where x is considered the lower or upper LOQ, respectively).

SARS-CoV-2 viral load results that are below LOQ but have a positive signal will be reported as "< LOQ SARS-CoV-2 detected" and those negative results will be reported as "No SARS-CoV-2 detected". The data will be imputed as follows:

• A value of half of the LOQ will be used to calculate descriptive statistics if the datum is reported as "< LOQ SARS-CoV-2 detected".

• A value of half of the limit of detection (LOD) will be used to calculate descriptive statistics if the datum is reported as "No SARS-CoV-2 detected".

Refer to Table 13-3 for more details on the viral load samples LOQ and LOD. Participants with negative viral load at baseline are not included in the viral load analysis.

Any SARS-CoV-2 viral load samples collected on or after the participants are receiving additional COVID-19 treatments (see Table 13-1) will be excluded from the viral load analysis.

For participants who had received IV RDV prior to the enrollment of this study, their viral loads will be excluded from the analysis.

Base 10 logarithm transformation will be used for analyzing SARS-CoV-2 viral load.

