- For baseline, the last nonmissing value on or prior to the first dosing date (and time, if available) of study drug will be selected, unless specified differently. If there are multiple records with the same time or no time recorded on the same day, the baseline value will be the average of the measurements for continuous data, or the measurement with the lowest severity for categorical data.
- For postbaseline values (other than PCR negative confirmation):
 - The record collected on the day closest to the nominal day will be selected.
 - If there are 2 days equidistant from the nominal day, the later day will be selected.
 - If there is more than 1 record on the selected day, values will be selected for analysis as follows:
 - For PCR, if there is more than 1 record on the selected day, the latest value will be selected. If there are multiple records with the same time or no time recorded on the same day, the geometric mean value (copies/mL) will be taken.
 - For other parameters, if there is more than 1 record on the selected day, the average will be taken for continuous data and the worst severity will be taken for categorical data, unless otherwise specified.
- For postbaseline values of PCR negative confirmation:
 - Use all available data to derive negative confirmation except if there are multiple records on the same day in which case the worst value will be used for negative confirmation for that day.
 - The record closest to the nominal day for that visit will be selected.
 - If there are 2 records that are equidistant from the nominal day, the later record will be selected.

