6.2.2. Analysis of Secondary Endpoints

The FAS will be the primary analysis set for secondary efficacy endpoints. No formal statistical testing is planned.

Clinical improvement based on scoring using the 7-point Ordinal Scale

For each cohort and overall total, clinical status and change from Baseline in clinical status by Study Day as well as last available assessment will be summarized by the number and percentage of participants for each category. It should be noted that the main timepoint of interest for this endpoint is Day 10. In addition, a stacked bar chart will also be provided for each cohort and overall total depicting the percentage of participants for each category by Study Day. Furthermore, descriptive statistics for change from Baseline in clinical status by Study Day and last available assessment will also be provided for each cohort and overall total. Time to clinical improvement (days) will be modelled using a competing risk analysis. The competing event is death. Participants not achieving clinical improvement at the last assessment will be censored on the day of the last clinical assessment. In addition, the cumulative incidence from the competing risk analysis will also be graphically presented. The number and percentage of participants with clinical improvement will also be summarized by cohort and overall total.

Time to \geq 1-point improvement from baseline clinical status or discharged alive on the 7-point ordinal scale will be modelled using a competing risk analysis. The competing event is death. Participants not achieving \geq 1-point improvement at the last assessment will be censored on the day of the last clinical assessment. In addition, the cumulative incidence from the competing risk analysis will also be graphically presented. Furthermore, the number and percentage of participants with a \geq 1-point improvement or discharged alive based on the 7-point ordinal scale on Day 2 through Day 10 as well as last available assessment will be summarized by cohort and overall total.

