As oxygen support status will be collected only while the participant is in the hospital, if a participant is discharged alive and dies afterwards, the participant will be included only in the summary for participants discharged alive.

Change from baseline in SARS-CoV-2 viral load up to Day 10 or up to the first confirmed negative PCR result (whichever comes first)

Descriptive statistics for viral load and change from baseline in viral load will be provided by cohort and overall total for the following:

- Day of discharge and each study day up to Day 10 or up to the first confirmed negative PCR result (whichever comes first)
- Day of discharge and each study day up to Day 10

Separate summary tables will be provided for each sample type: (a) nasal/oropharyngeal samples, (b) nasopharyngeal/oropharyngeal samples, (c) endotracheal tube (ET) aspirates, and (d) rectal or fecal swabs.

Days to the first confirmed negative PCR result, where confirmed is defined by 2 consecutive negative PCR results

For each cohort and overall total, the number and percentage of participants with:

- At least 1 negative PCR result
- Confirmed negative PCR result

will be summarized separately for each sample type: (a) nasal/oropharyngeal samples, (b) nasopharyngeal/oropharyngeal samples, (c) ET aspirates, and (d) rectal or fecal swabs.

Time to first confirmed negative PCR result will be modelled separately for each sample type: (a) nasal/oropharyngeal samples, (b) nasopharyngeal/oropharyngeal samples, (c) ET aspirates, and (d) rectal or fecal swabs, using a competing risk analysis. The competing event is death. Participants not not achieving a confirmed negative PCR at the last assessment will be censored on the day of the last clinical assessment.

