- Time to ≥ 2 point improvement and time to ≥ 1 point improvement: if a participant did not experience the event of interest and did not die, the participant was censored at the last non-missing assessment date. Participants who died were considered to have experienced a competing event.
- Time to recovery: Participants not achieving recovery at the last assessment were censored on the day of the last assessment. Participants who died were considered to have experienced a competing event.
- Time to discharge from hospital: Participants not discharge at the last assessment were censored on the day of the last clinical assessment. Participants who died were considered to have experienced a competing event.

18) Details on the LOQ and LOD for the viral load samples are provided below.

Table 13-3.Viral Load Sample Details

Sample type	Limit of quantitation (copies/mL)	Limit of detection (copies/mL)
Nasal/oropharyngeal samples Nasopharyngeal/oropharyngeal samples ET aspirates	1018	925
Rectal or fecal swabs	488	306

- 19) Quantitative and categorical summary on SARS-CoV2 results and change from baseline in SARS-CoV-2 viral load up to Day 10 or up to the first confirmed negative PCR result (whichever comes first)
 - For quantitative summary (e.g., mean viral load, change from baseline etc.), "Inconclusive" SARS-CoV2 result is set to missing
 - For categorical SARS-CoV2 summary, 3 categories will be included, i.e. Positive, Inconclusive, Negative
 - Positive = Any numeric result or "< 1018cp/mL SARS-CoV-2 detected" (for Nasal/oropharyngeal samples, Nasopharyngeal/oropharyngeal samples, or ET aspirates) or "< 488cp/mL SARS-CoV-2 detected" (for rectal or fecal swabs)
 - Negative = "No SARS-CoV2 detected"
 - Inconclusive = "Inconclusive"

20) Days to the first confirmed negative PCR result

- Categorical SARS-CoV2 and SARS-CoV2 negative summary will be separated out by sample type. There will be no combined positive or negative category using 2 or 3 sample types.
- Confirmed negative PCR result is defined as 2 consecutive negative results, or negative at last available sample for participants who completed or discontinued from study. Notice 2 negative results from the same day do not equal confirmation.
- For a negative SARS-CoV2 confirmation, "Inconclusive" SARS-CoV2 result will not be considered as missing thus a "Negative" followed by a "Inconclusive" is NOT a confirmed negative PCR result.

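### PCR outputs are run by sample type, but the baseline-negative exclusion names no specimen and is not tied to the negative-PCR endpoints, so a specimen already negative at baseline can be counted as clearing

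*SAP*

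**What the plan says.** Section 3.7 sets the only exclusion for children without detectable virus at the start: "Participants with negative viral load at baseline are not included in the viral load analysis". It does not say in which specimen the baseline must be negative, or whether the negative-PCR endpoints belong to the analysis it refers to.

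Section 6.2.2 treats change in viral load and days to first confirmed negative PCR under two separate headings, each by four sample types: nasal/oropharyngeal, nasopharyngeal/oropharyngeal, endotracheal aspirate, and rectal or fecal swab. For change in viral load, "Separate summary tables will be provided for each sample type". For the other endpoint, "Time to first confirmed negative PCR result will be modelled separately for each sample type", with death as the competing event. Appendix 3 item 20 adds: "There will be no combined positive or negative category using 2 or 3 sample types".

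The confirmed-negative event is defined in Appendix 3 item 20 as "2 consecutive negative results, or negative at last available sample" for participants who completed or left the study. Section 3.8.3 gives its data-selection rule: "Use all available data to derive negative confirmation except if there are multiple records on the same day".

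The analysis set is given in Section 6.2.2: "The FAS will be the primary analysis set for secondary efficacy endpoints". Section 3.1.2 sets no PCR condition for it: "The Full Analysis Set (FAS) includes all enrolled participants who received at least 1 dose of study drug".

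**The concern.** A specimen that was not positive at baseline has nothing to clear. Eligibility (Section 1.2) rests on a PCR done at a local laboratory, with screening up to 2 days before Day 1. That does not guarantee a positive Day 1 result in each study specimen. A child may be positive in one sample type and negative in another.

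If such a child stays in the analysis of the negative specimen, the share confirmed negative is too high and the cumulative incidence curve rises too early. There is no control arm in which the same distortion would occur and could be compared. The reported proportion and time are themselves the evidence on the antiviral secondary objective.

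The change-from-baseline tables have a related gap. If the exclusion is not applied within each specimen, a child positive in one specimen and negative in another enters the second table with a baseline imputed at half the limit of detection. No decline can be measured from that value.

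**Working it through.** The SAP states no figure on this point, so there is nothing to reproduce. The check is textual, followed by an illustration of size.

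**Step 1: does any rule require a positive baseline in the specimen analysed?**

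- Definition (Section 6.2.1 and Appendix 3 item 20): two consecutive negatives, or a negative last sample. No earlier positive is required. Two negatives on one day do not confirm, and a negative followed by an inconclusive result does not confirm.
- Data selection (Section 3.8.3): all available data, with the worst value taken where one day has several records. No baseline condition.
- Summaries (Section 6.2.2): counts with at least one negative and with a confirmed negative, by sample type. No baseline condition.
- Censoring (Section 6.2.2 and Appendix 3 item 20): every participant without the event is censored. Baseline negatives are not set aside.
- Analysis set (Sections 3.1.2 and 6.2.2): enrolled with at least one dose. No PCR condition.
- Section 3.7: the single exclusion, per participant, with no specimen and an undefined scope.

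The Section 3.7 sentence is therefore the only text that could keep out a specimen that was negative at baseline.

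**Step 2: what can that sentence mean?**

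1. It covers only the quantitative viral load tables. A child negative in a specimen at baseline then stays in that specimen's negative-PCR outputs.
2. It covers all PCR outputs, and any negative specimen removes the child. Valid data from a positive specimen are then lost.
3. It covers all PCR outputs, and only a child negative in every specimen is removed. The miscount in reading 1 remains for children with mixed results.
4. It covers all PCR outputs and is applied within each sample type. There is then no miscount.

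The SAP does not choose among these. Two programmers could follow it and produce different tables.

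**Step 3: size under readings 1 and 3.**

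Inputs, all assumed: f is the share negative in that specimen at baseline and still counted in it; these children stay negative; p is the true clearance among those positive at baseline.

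Reported share = f + (1 - f)p. Excess over p = f(1 - p).

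| f | p = 30%: reported (excess) | p = 50%: reported (excess) |
|---|---|---|
| 10% | 0.10 + 0.90 × 0.30 = 37% (+7 points) | 0.10 + 0.90 × 0.50 = 55% (+5 points) |
| 25% | 0.25 + 0.75 × 0.30 = 47.5% (+17.5 points) | 0.25 + 0.75 × 0.50 = 62.5% (+12.5 points) |
| 50% | 0.50 + 0.50 × 0.30 = 65% (+35 points) | 0.50 + 0.50 × 0.50 = 75% (+25 points) |

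In counts, take the minimum total of 52 from Section 1.3 and suppose all 52 gave the specimen (also an assumption). With f = 50% and p = 50%, 26 are negative at baseline and 13 of the other 26 clear. The report reads (26 + 13)/52 = 75%. Restricted to baseline positives it reads 13/26 = 50%.

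**Step 4: timing.** Samples are planned on Days 1, 3, 5, 7 and 10. A child negative throughout, with samples on Days 3 and 5, meets the definition on those two. The SAP does not say which of the two negatives dates the event, so it falls on Day 3 or Day 5, early on the curve in either case.

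**The case against.** The strongest reply is that the SAP uses the term viral load for the RT-qPCR test as such. Section 3.7 lists negative results among the viral load results, Table 3-3 labels every PCR visit that way, and Appendix 3 uses the same label for all sample types. On that usage the exclusion reaches the negative-PCR endpoints. With no status combined across specimens and every table split by sample type, applying it within each table is the sensible course. The full analysis set does not settle the matter, since it is also the set for change in viral load, where the exclusion plainly applies on top of it.

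Much of this stands. The reading is plausible, and a careful programmer might adopt it. It is nowhere stated, though, and the confirmed-negative endpoint has its own heading, definition, data selection and censoring, none of which refers back to the exclusion. The next sentence in Section 3.7 excludes samples rather than participants, so the SAP does word a rule at sample level where it means one.

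A reader might infer more than the text supports:

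- That a baseline-negative child becomes a confirmed clearance at the first postbaseline swab. Confirmation needs two consecutive negatives or a negative last sample. A single negative suffices only for the count with at least one negative.
- That rectal or fecal swabs are affected most. The SAP gives no positivity rate by specimen.
- That every reading yields a wrong result. Removing the whole participant mainly loses data, and the within-specimen reading has no miscount.

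**Conclusion.** The point holds as a defect in a rule. The only baseline-negative exclusion identifies neither the specimen nor the outputs it governs, and the text allows a specimen negative at baseline to be counted as cleared. Where that happens, the bias goes one way: a higher share negative and earlier times. The excess is f(1 - p), or 5 to 35 points over the range shown. It rests on assumed f and p and on baseline negatives staying negative. The SAP supplies none of these, so the actual size cannot be known from it.

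The consequence is limited. The endpoints are secondary and descriptive, with no formal testing (Sections 3.5 and 6.2.2) and no primary efficacy endpoint (Section 6.1). The correction is still worth making, because it decides who is in the denominator of a single-arm estimate.

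**What to change.** Replace the exclusion sentence in Section 3.7 with text such as:

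*For each sample type, the change-from-baseline viral load summaries, the negative-PCR counts and the time to first confirmed negative PCR include only participants whose baseline result in that same sample type is Positive as defined in Appendix 3 item 19. A negative baseline in one sample type does not exclude the participant from another. The numbers with a negative, inconclusive or missing baseline are reported for each sample type.*

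The last sentence is needed because requiring a Positive baseline also removes children whose baseline is inconclusive or missing, for example an endotracheal aspirate from a child intubated after Day 1. That loss should be visible.

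The cost is a short text change, one population flag per sample type and a row of counts. Fewer participants will be analysed per sample type. If the SAP is not reopened, Section 1 provides for documenting later changes in the clinical study report.
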